Soft multifocal contact lenses, (MFCLs), are a great option for new and established presbyopes, offering good vision performance with the added benefit of improved cosmesis and convenience compared to spectacles, and provide them the flexibility to change-up their vision correction. CL manufacturers are continually innovating in this area, with the increased availability of soft MFCLs with novel designs in a range of replacement frequencies from daily disposable to monthly replacement, and different materials including silicone hydrogels.

Therefore, CooperVision is interested in comparing the short-term clinical performance and subjective acceptance of Clariti Monthly Multifocal, (**LENS A**), to the Clariti 1-Day Multifocal, (**LENS B**), silicone hydrogel contact lenses. A non-dispensing fitting study is proposed to evaluate the short-term clinical performance of these lenses.

2 Study Objective

The aim of this non-dispensing fitting study is to evaluate the short term lens fit, vision performance and patient subjective experiences of the Clariti Monthly Multifocal when compared to the Clariti 1-Day Multifocal after 15 minutes of daily wear.

The primary outcome variable is:

Subjective comfort ratings on insertion (assessed by subjects)

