3.1 Study Hypothesis

- Null hypothesis (Ho): There is no difference in clinical performance and subjective assessments between multifocal lens types.
- Alternative hypothesis (H1): There is a difference in clinical performance and subjective assessments between multifocal lens types.

4 Study Design

This is a 40-subject, single-blind, (participant masked), interventional, prospective, direct refit, bilateral wear study. It is anticipated that this study will involve 4 visits as follows: **V1**: (BL/trial fit/lens order), **V2**: Dispense / evaluate P1. **V3**: 15 minutes. Evaluate P1/Dispense P2. **V4**: 15 minutes. Evaluate P2 / study exit.

5 Investigational Sites

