8.1 Participants

Habitual soft contact lens wearers who currently wear multifocal contact lenses, sphere lenses for monovision, or sphere lenses for distance vision correction and use spectacles for near vision correction, that provide written informed consent and meet the protocol entrance criteria. Subjects will be recruited from the National Autonomous University School of Optometry databases who agree to voluntarily participate in the study (Appendix 2, timeline). All subjects will be screened to determine study eligibility. Each subject will be given a unique ID number. Additionally, all subjects must meet the study inclusion and exclusion criteria listed below.

Inclusion criteria

A person is eligible for inclusion in the study if he/she:

- 1. Is at least 42 years of age and has full legal capacity to volunteer.
- 2. Has read and signed an information consent letter.
- 3. Self-reports having a full eye examination in the previous two years.
- 4. Anticipates being able to wear the study lenses for at least 8 hours a day, 5 days a week.
- 5. Is willing and able to follow instructions and maintain the appointment schedule.
- 6. Habitually wears multifocal soft contact lenses, or sphere lenses for monovision, or sphere lenses for monovision, or sphere lenses for distance vision correction and use spectacles for near vision correction, for the past 3 months minimum.
- 7. Has refractive astigmatism no higher than -0.75DC.
- 8. Is presbyopic and requires a reading addition of at least +0.75D and no more than +2.50D.
- 9. Can be fit and achieve binocular distance vision of at least 20/30 Snellen (or +0.20 logMAR) which participants also deem to be 'acceptable', with the available study lens parameters (powers +4.00 to -6.00DS) (see Table 1).

Exclusion Criteria

A person will be excluded from the study if he/she:

- 1. Is participating in any concurrent clinical or research study.
- 2. Has any known active* ocular disease and/or infection that contraindicates contact lens wear.
- 3. Has a systemic condition that in the opinion of the investigator may affect a study outcome variable.
- 4. Is using any systemic or topical medications that in the opinion of the investigator may affect contact lens wear or a study outcome variable.
- 5. Has known sensitivity to the diagnostic sodium fluorescein used in the study.
- 6. Self-reports as pregnant, lactating or planning a pregnancy at the time of enrolment.

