10.1 Statistical analysis

Summary statistics will be produced, (e.g., mean, standard deviation), by the principal investigator ([name]). Differences between lenses will be compared using Paired t-tests. Paired t-tests /analysis of variance for normal (interval/continuous) data, Wilcoxon's signed ranks test for non-normal (ordinal) data, chi-squares test for nominal data. A Chi-Square test will be used to evaluate lens preference questions. All participants who are evaluated in the study will be used in the analysis. In the event of missing data individual number of points will be excluded in the analysis and not extrapolated from the collected data. The critical alpha level for statistical significance will be set at p \leq 0.05, with adjustment for multiple comparisons.

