APPENDIX 5 - GRADING & MEASUREMENT SYSTEM

Variable	Assessment Method	Grading/Measurement System		
Wearing Times				
Average # of days lenses worn in a week	Enter the number of days lenses are worn during the week.	Days per week		
Average Daily Wearing Time	Typical time of day when lenses inserted and removed.	Time of day to nearest half hour		
Average # of hours of wear per day	Enter the number of hours lenses are worn per day.	Hours per day		
Average Comfortable Wearing Time	Typical time of day when subject first experiences LENS Awareness or irritation.	'Does CL comfort deteriorate during wear?' (tick- box). If yes, record time of day to nearest half hour when first aware of lenses		
Typical Removal Time	Typical time of day when subject removes the lens.	Time of day to nearest half hour		
Subjective	Assessments (Questions asked by t	he investigator and recorded)		
Comfort, dryness, handling, lens fit, vision satisfaction.	Assessed by subject on a 0-10 scale.	0-10 scale Comfort: (10= can't feel) Dryness: (10=no dryness) Handling: (10=very easy) Fit stability (10=very stable) * Vision: (10=very satisfied)		
Vision Quality	Assessed by subject on a 0-10 scale.	Vision quality: (10=Excellent vision, totally sharp)		
Night Vision Quality	Assessed by subject on a 0-10 scale.	Vision quality: (10=Excellent vision, totally sharp)		
Vision Stability	Assessed by subject on a 0-10 scale.	Vision stability: (10=perfectly stable, not fluctuating, changing)		
Satisfaction	Subject's assessment of various symptoms on a 4-point Likert scale.	Completely satisfied Somewhat satisfied Somewhat dissatisfied Completely dissatisfied		
Preference	Subject's preference for one of two contact lenses.	Forced choice: Study lenses or Habitual		
Vision				
Distance VA – High contrast	Measured using Snellen or logMAR chart.	Snellen or logMAR visual acuity (VA) to nearest letter.		
Lens Surface assessed using slit lamp				
Front Surface Wettability	Lens surface viewed with a slit lamp, white diffuse light and broad beam under low-medium magnification.	0 – 4 0=poor 4=excellent		

Variable	Assessment Method	Grading/Measurement System		
	Lens surface deposits assessed us	ing the slit-lamp		

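### The only readable preference coding in Appendix 5 (study lenses or habitual) has no LENS A or LENS B category, so it does not match the trial's only stated contrast

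*Combined protocol and SAP*

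**What the plan says.** **Coding.** In Appendix 5 (Grading & Measurement System), the Preference row describes a choice between two contact lenses that it does not name. It gives the response as "Forced choice: Study lenses or Habitual". No other preference coding can be read in the document.

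**Contrast.** The Introduction states an interest in "comparing the short-term clinical performance and subjective acceptance of Clariti Monthly Multifocal" (LENS A) against the 1-Day lens (LENS B), and section 2 repeats that comparison. The alternative hypothesis in section 3.1 is "There is a difference in clinical performance and subjective assessments between multifocal lens types".

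**Analysis.** Section 10.1 says "Differences between lenses will be compared using Paired t-tests" and then "A Chi-Square test will be used to evaluate lens preference questions". It names neither the response categories nor the null proportion.

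**Habitual correction.** Inclusion criterion 6 in section 8.1 admits a mix. It begins "Habitually wears multifocal soft contact lenses, or sphere lenses for monovision" and goes on to distance spheres worn with reading spectacles.

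**Wearing order.** Section 8.3 has every participant fitted with LENS A before LENS B. Section 8.2.1 instead assigns the first pair from a table in Appendix 3, and that appendix is titled as a randomization table.

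**The concern.** The row asks about a comparison that no readable objective or hypothesis makes. A subject who answers for the study lenses may favour LENS A, LENS B or both, and the answer does not show which. The comparator is also mixed: habitual multifocals for some, monovision for others, distance spheres plus spectacles for the rest.

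If this is the only preference question and it is asked once, the test planned in 10.1 can be computed but says nothing about the two lenses being compared. No later analysis can recover a choice that was not asked for.

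Wearing order matters as well. If LENS A is always worn first, even a well-coded A-versus-B preference cannot be separated from a tendency to favour the first or the second pair.

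**Working it through.** **1. The plan's own figure.** Section 10.2 gives a power of 0.800497 for comfort at insertion: paired t-test, n = 40, difference 1.0, SD of differences 2.2, two-sided alpha 0.05. The noncentrality is (1.0/2.2) × √40 = 2.875 on 39 df, and the power is 0.8005. The figure reproduces. It concerns comfort only; the document gives no figure for preference.

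**2. The sections side by side.**

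| Place | Contrast |
|---|---|
| Sections 1 and 2 | LENS A v LENS B |
| Section 3.1 | between the multifocal lens types |
| Section 10.1, differences | between lenses, paired |
| Section 10.1, preference | not named |
| Appendix 5, Preference | study lenses v habitual |

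Only the last row departs from A versus B.

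**3. Asked once as coded.** The data are two counts, study and habitual, summing to 40. Neither contains a count for A or for B, so no A-versus-B proportion or test can be formed.

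**4. Asked after each pair.** The document does not say when the item is asked. If it is asked twice, each subject gives an A-versus-habitual and a B-versus-habitual answer, and only subjects whose answers differ inform A versus B. Let p be the chance of choosing the study lens each time and P11 the chance of choosing it both times. The expected number of differing subjects is 40 × 2 × (p − P11). P11 comes from a bivariate normal with latent correlation ρ. Both p and ρ are assumptions.

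| p | ρ = 0.5 | ρ = 0.7 | ρ = 0.85 |
|---|---|---|---|
| 0.70 | 11.5 | 8.8 | 6.1 |
| 0.90 | 5.4 | 4.3 | 3.0 |

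Example: for p = 0.70 and ρ = 0.5, P11 = 0.557, so 80 × (0.700 − 0.557) ≈ 11.5.

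**5. A direct choice between the pairs.** All 40 subjects contribute. With k choosing one lens, the one-sample chi-square against 50:50 is (2k − 40)²/40.
- k = 26: 3.6, p = 0.058.
- k = 27: 4.9, p = 0.027 (exact binomial 0.038).

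The smallest significant split at an unadjusted 0.05 is therefore 27:13. Power for a true preference of 65%, 70% or 75% is 44%, 70% or 90%. These rates are illustrations.

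**6. Wearing order.** Suppose the lenses are equally liked and a share q of subjects choose one particular pair because of its position alone. Under the 27:13 rule, the chance of a significant lens preference is:

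| q | LENS A always first | Order balanced 20:20 |
|---|---|---|
| 0.60 | 21% | 3.5% |
| 0.65 | 44% | 3.0% |
| 0.70 | 70% | 2.4% |

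The fixed-order column is the two-tailed Bin(40, q) probability. The balanced column uses the sum of Bin(20, q) and Bin(20, 1 − q). The values of q are assumptions.

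**The case against.** **The question may exist elsewhere.** Most items in sections 8.3.2 to 8.3.5 are blanked, and Appendix 6 shows no forms. Section 10.1 speaks of preference questions in the plural, while Appendix 5 shows one row. This stands. A reader might infer that the trial never asks for an A-versus-B preference, but the documents do not support that. What they show is one appendix row that does not fit the trial's comparison.

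**Preference is named only in 10.1.** The objective speaks of subjective experiences and the hypothesis of subjective assessments. This also stands. A reader might infer that the objective and hypothesis require an A-versus-B preference; they do not say so. A versus B is inferred because it is the only contrast stated.

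**The item is not always uninformative.** Asked after each pair, it gives some indirect information (step 4). To say flatly that it cannot inform A versus B would be too strong.

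**The row is coherent as a study-versus-habitual question, and Appendix 5 looks like a general list.** The appendix also covers axis-mark orientation and rotational recovery, although Table 1 lists only sphere and add powers, and days of wear per week in a 15-minute study. The row may have been carried over. That weakens it as evidence of what is collected, but it remains the only readable definition of the outcome and still needs correcting.

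**A wider fault in 10.1.** A reader might infer from "chi-squares test for nominal data" that outcomes recorded on both lenses will be tested as if unpaired. The phrase does not exclude a paired form, so no such error is shown.

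**Conclusion.** The preference coding is wrong as written for the trial's stated comparison and should be corrected. If it is followed literally and asked once, the A-versus-B information is nil. If it is asked after each pair, it comes from about 6 to 11 of 40 subjects when 70% choose the study lenses each time, and 3 to 5 when 90% do, with latent correlations of 0.5 to 0.85 assumed.

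The consequence is limited. Preference is not among the primary endpoints in the synopsis or section 2, and nothing here touches the comfort analysis or the 40-subject sample size. Whether A-versus-B preference data would really be lost depends on the unseen case report form. If the form holds a direct question, the defect is a conflict between that form and Appendix 5.

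The disagreement on wearing order is a separate design matter. It bears on this point only because a fixed order makes first pair and LENS A the same label. The percentages in step 6 depend on the assumed order effect and are not a forecast. The 27:13 threshold is unadjusted: 10.1 promises testing "with adjustment for multiple comparisons" but gives no method.

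**What to change.** **Appendix 5, and the case report form if it matches:** code preference as a forced choice between first pair and second pair, asked once at V4 after both pairs have been worn, and decoded to LENS A or LENS B. Keep any study-versus-habitual question as a separate, labelled item. If the form already has an A-versus-B item, correct the Appendix 5 row to agree with it.

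**Section 10.1:** state that the preference test is a one-sample chi-square against 50:50.

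**Sections 8.3, 8.2.1 and Appendix 3:** reconcile LENS A first for everyone with the assignment or randomization table. If LENS A is always first, report preference as confounded with wearing order.

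**Cost:** a changed response option, one V4 question if it is not already on the form, a decoding rule, a sentence in 10.1, and an edit to settle the wearing order. The coding and analysis changes need no extra visits or subjects.

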10.2 Sample size

The sample size was calculated using data of lens comfort at insertion on day 1 collected in a previous study that evaluated the clariti 1day multifocal lens (CooperVision, data on file). Figure 1 shows the sample size determination for a paired t-test, (alpha=0.05), in order to detect a difference Assuming a standard deviation of 2.2, a sample size of 40 completed subjects provides 80% power to detect a difference of 1.0 points on a 0 - 10 scale in subjective comfort ratings at insertion.

Paired t Test

Testing mean paired difference = 0 (versus \neq 0) Calculating power for mean paired difference = difference α = 0.05 Assumed standard deviation of paired differences = 2.2

Results			
Difference Sam	ple Size Targ	et Power A	tual Power
1	40	0.80	0.800497
1 1	40 45	0.80 0.84	0.800497 0.846619

11 Data Quality Assurance

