Front Surface Deposits	Lens surface deposits viewed with a slit lamp, white diffuse light and broad beam under low-medium magnification.	 Clean, no deposits 5 or less small deposits (<0.1 mm) > 5 deposits of <0.1 mm size or film covering 25-50% of surface Deposits of between 0.1 and 0.5 mm or film covering 50-75% of surface Deposits of 0.5 mm or larger or film covering more than 75% of surface 		
Lens Fit- assessed using slit lamp				
Lens Centration	Lens centration will be recorded by degree and direction in the primary position.	0 Centered - optimal 1 Decentered slightly 2 Substantially decentered (≥0.5mm) If decentered, direction(s) will be recorded as: Superior, Inferior, Nasal, Temporal		
Corneal Coverage	Assessed in primary gaze.	Y Yes, full corneal coverage at all times N No, incomplete corneal coverage		
Post-Blink Movement	Assessed immediately after the blink - lower lid to be depressed only if necessary, for observation.	0 Insufficient, unacceptable movement 1 Minimal, but acceptable movement 2 Optimal movement 3 Moderate, but acceptable movement 4 Excessive, unacceptable movement		
Lens orientation in primary position of gaze	Slit lamp, with 10x magnification. Nasal mislocation is recorded as (+) and temporal as (-)	Mislocation of the axis mark on the lens relative to the 6 o'clock position, zero rotation, measured in degrees.		
Overall stability	Slit lamp, with 10x magnification.	(0–4 scale), where 0=very poor, 4= excellent		
Rotational recovery in degrees after 60 seconds	Slit lamp, with 10x magnification.	LENS Ability to return to its original position measured 60 seconds after manually rotating the lens 45° degrees temporally. Rotational recovery (RR) is assessed by manually rotating the lens 45° temporally from the primary gaze orientation (PGO) and allowing one minute (60 seconds) for the lens to recover. The absolute difference between the position of the lens following the recovery period and the PGO is taken as the measure of interest.		
Overall Fit Acceptance	Assessed by the Investigator based on lens fit alone (i.e., not comfort or vision).	0 Should not be worn 1 Borderline but unacceptable 2 Min. acceptable, early review 3 Not perfect but OK to dispense 4 Perfect		

Variable	Assessment Method	Grading/Measurement System		
Biomicroscopy				

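### Post-blink movement is best at the middle grade, but the only rule in section 10.1 that fits it is the general ordinal test, which on the raw grade compares how much the lenses move, not how acceptably

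*Combined protocol and SAP*

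**What the plan says.** Appendix 5, under Lens Fit, grades post-blink movement from 0 to 4: "0 Insufficient, unacceptable movement 1 Minimal, but acceptable movement 2 Optimal movement 3 Moderate, but acceptable movement 4 Excessive, unacceptable movement". The other ordered fit grades in that table (centration, overall stability, Overall Fit Acceptance) each run in one direction between best and worst.

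Section 10.1 chooses tests by type of data, not by variable. It opens with "Differences between lenses will be compared using Paired t-tests" and then allots t-tests or ANOVA to normal data and "Wilcoxon's signed ranks test for non-normal (ordinal) data, chi-squares test for nominal data". For description, "Summary statistics will be produced, (e.g., mean, standard deviation" and so on. Significance is set at 0.05 "with adjustment for multiple comparisons", by a method it does not name. No visible text recodes post-blink movement, collapses it, or declares it nominal.

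Section 2 gives the aim as to "evaluate the short term lens fit, vision performance and patient subjective experiences" of one lens compared with the other. The primary outcome there is comfort on insertion.

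**The concern.** The grade is ordered by amount of movement, but its quality peaks at 2. On the raw grade, a move from 1 to 2 (better) and a move from 2 to 3 (worse) both count as +1, and a 0 in one subject offsets a 4 in another. A signed-rank or paired t comparison of raw grades therefore estimates a shift in amount of movement.

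Lens fit is the first item in the study aim, and a reader of the report will take a movement comparison as evidence on fit. Two errors are then possible. A non-significant result could be read as equivalent fit when one lens has many more unacceptable fits at both ends. A significant result could be read as a difference in fit quality when the lenses are equally acceptable but sit on opposite sides of the optimum.

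**Working it through.** **The plan's own figure.** The documents give no power or expected distribution for post-blink movement. The only power figure, in section 10.2, is for comfort ("Testing mean paired difference = 0", two-sided). With noncentrality (1.0/2.2) × √40 = 2.875 on 39 degrees of freedom, power is 0.8005, matching the stated 0.800497. It does not bear on this point except for n = 40.

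**Inputs.** From the documents: the 0–4 scale, the signed-rank test, 40 pairs, two-sided 0.05. Assumed: the grade distributions, one value per subject per lens, lenses independent within subject, no multiplicity adjustment. Let d = |grade − 2|, so d = 0 is optimal, 1 acceptable, 2 unacceptable.

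**A constructed case.** One lens: all 40 subjects at grade 2. Other lens: 10 at 0, 10 at 4, 20 at 2.
- Raw: the means are 2.0 and 2.0. The non-zero differences are ten of −2 and ten of +2, so the positive and negative rank sums are both 10 × 10.5 = 105, and p = 1.0. The paired t-test also gives p = 1.0.
- On d: all 20 non-zero differences have the same sign, and the signed-rank p = 7.7 × 10⁻⁶.
- Unacceptable versus acceptable: 20 discordant pairs, all one way. Exact McNemar p = 2 × 0.5²⁰ = 1.9 × 10⁻⁶.
- Raw SD: √(20 × 4/39) = 1.43 against 0.

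**Main simulated case.** Grades 0–4 at 2.5/15/65/15/2.5% for one lens and 15/15/40/15/15% for the other, so 5% versus 30% unacceptable.
- Raw means: 0.15 + 1.30 + 0.45 + 0.10 = 2.0 and 0.15 + 0.80 + 0.45 + 0.60 = 2.0.
- Mean d: 2 × 0.05 + 0.30 = 0.40 and 2 × 0.30 + 0.30 = 0.90.

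Over 4,000 replicates the rejection rates were 4.8% (raw signed-rank), 86.5% (signed-rank on d) and 80.2% (exact McNemar). Repeat runs agreed to within about two points.

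**How it changes with the assumptions.**

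| Grades 0–4, % (one lens vs other) | Raw | On d | McNemar |
|---|---|---|---|
| Balanced: 2.5/15/65/15/2.5 vs 15/15/40/15/15 | 5% | 87% | 80% |
| Mostly tight: 2.5/15/65/15/2.5 vs 27.5/15/40/15/2.5 | about 65% | as above | as above |
| Wholly one-sided: 0/10/80/10/0 vs 30/10/50/10/0 | 95% | 98% | 99% |
| Grades 1–3 only: 0/10/80/10/0 vs 0/25/50/25/0 | 5% | about 82% | none |
| Mirror images: 0/30/65/5/0 vs 0/5/65/30/0 | 98% | 5% | none |
| Failures rare: 1/12/74/12/1 vs 2.5/15/65/15/2.5 | not needed | 15% | 0.7% |

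In the second row, d has the same distribution as in the first, so the last two columns carry over. In the fourth and fifth rows no fit is unacceptable, so McNemar has nothing to test. In the fifth row both lenses have mean d = 0.35, and the raw means are 0.30 + 1.30 + 0.15 = 1.75 and 0.05 + 1.30 + 0.90 = 2.25.

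With 20% unacceptable, split evenly between the two ends, the power on d is 46% to 49% or about 73%, depending on how the other grades are split. The raw test stays near 5%.

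**The case against.** **Attribution.** A reader might infer that 10.1 prescribes the signed-rank test on the raw movement grade. It does not: it never mentions the variable, and its labels would also permit a categorical analysis. This stands. What the documents show is that the only fitting rule is the general ordinal one and that nothing modifies it.

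**Use in this trial.** The procedure lists in section 8.3 are largely blank in the available text, so the visits at which movement is graded cannot be seen. Appendix 5 also includes items that sit oddly with a 15-minute study of lenses for which Table 1 lists no cylinder, such as weekly wearing days and axis-mark rotation. This limits how much weight the variable can be given. It does not supply an analysis rule.

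**Coverage elsewhere.** Overall Fit Acceptance is judged on fit alone, runs from worst to best and suits the signed-rank test. A lens with many unacceptable movement grades should score poorly there. So the tempting claim that the trial would miss a large difference in fit is not supported. The gap is in the movement result itself.

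**A legitimate question.** Amount of movement is worth comparing, and the alternative hypothesis in 3.1 is simply that the lenses differ. A significant result for mirror-image lenses is therefore a true finding about movement, not a false positive. It misleads only if read as fit quality.

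**Extremity.** Full cancellation needs balanced failures. The lenses share material, base curve and diameter, and both are trial-fitted and optimised at Visit 1, so grades 0 and 4 may be rare. This stands for the 30% figure, which no document supports. But the same masking occurs with grades 1 to 3 alone.

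**Visibility.** The lenses would not look identical in every summary. The SD would differ (1.43 against 0 in the constructed case), as would a frequency table. The SD is only an example summary, though, and no frequency table is promised.

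**Conclusion.** The point holds as a gap between scale and test. Following 10.1 as written, post-blink movement would be compared on a raw grade that does not measure fit quality. With roughly balanced tight and loose fits, power to detect a difference in acceptability stays at about 5%, against about 87% on |grade − 2| and about 80% for exact McNemar at an assumed 5% versus 30% unacceptable. The raw test recovers to about 65% when the same excess is mostly in one direction, and to 95% in a wholly one-sided case.

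These figures rest on assumed distributions, independent lenses, one value per subject and an unadjusted 0.05. If unacceptable fits are rare, no analysis of this variable has much power at n = 40.

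The importance is low to moderate. The measure is not primary, the sample size does not depend on it, and another fit scale covers part of the ground. The documents do not support reading this as a threat to the primary result or to the fit assessment as a whole.

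**What to change.** In 10.1, name post-blink movement and state that:

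1. the between-lens comparison uses |grade − 2| with the signed-rank test;
2. the full 0–4 distribution is tabulated for each lens, with the proportion unacceptable (0 or 4), and an exact McNemar test of that proportion is supportive only;
3. the mean raw grade is not interpreted as fit quality.

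Appendix 5 already takes this approach for rotational recovery, which is scored as an absolute departure from the reference position.

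The cost is a few lines of text and no new data. The test no longer distinguishes too tight from too loose and weights them equally, but the distribution table keeps the direction. Because the multiplicity method is unnamed, the text should also say that the supportive McNemar test is outside the adjusted set, so that one comparison of this variable replaces another and none is added.
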